1.2. Study Design

This study is a single-arm, open-label, multicenter study of RLYB212 in HPA-1b/b pregnant participants at higher risk for the occurrence of HPA-1a alloimmunization and FNAIT. A laboratory testing paradigm will be applied at screening to identify women at higher risk for HPA-1a alloimmunization. Study IPA2202 is comprised of three phases: a two-part screening phase, an antenatal treatment phase, and a postpartum follow-up phase ([Figure 1](#)). Study duration for each participant is anticipated to be around 44 weeks, inclusive of the screening visits through the Week 10 postpartum visit. For each child born during the study, the study duration is anticipated to be around 12 months.

[figure not shown]
For the non-interventional (observational) sub-study (IPA2202A), the same two-part screening phase for the intervention, as applicable, is followed by a postpartum follow-up phase. The sub-study duration is anticipated to be around 44 weeks, inclusive of the screening visits through the Week 10 postpartum visit.

The overall design of the Phase 2 study, including the non-interventional (observational) sub-study, is presented in [Figure 1](#).

The study intervention, RLYB212, will be administered to participants via SC injection using vial and syringe in accordance with the study protocol. The RLYB212 dose regimen is comprised of an initial (loading) dose of 0.12 mg no later than GW 16 followed by maintenance (repeat) doses of 0.06 mg every 4 weeks (Q4W) \pm 3 days throughout the pregnancy and with a final 0.06 mg dose within 24 hours (\pm 24 hours) of parturition. The dose regimen may be adjusted empirically as additional participants are enrolled in the study, as described in the study protocol.

Parexel International
Statistical Analysis Plan

Figure 1 Overall Study Design (Interventional and Non-interventional [Observational])

FNAIT = fetal and neonatal alloimmune thrombocytopenia; ICF = informed consent form; PK = pharmacokinetic; SC = subcutaneous. For Screening (Part 2)/ICF: Enrollment planned for 8 eligible participants for whom the pregnancy results in a live birth and who are evaluable for PK and safety assessments

Project Document Version No.: 2.0; Document Effective Date: Date of last signature

TP-GDO-WW-016-09

Effective Date: 22 Dec 21

Related to: SOP-GDO-WW-019

Page 12 of 70

Parexel International
Statistical Analysis Plan

2. Statistical Hypotheses

This study will be descriptive in nature. No statistical hypothesis testing is proposed. No formal interim analyses will be conducted. Preliminary data may be used for summary purposes and for communication with health authorities.

2.1. Multiplicity Adjustment

No hypotheses are planned to be formally tested using inferential statistics in this study; hence multiplicity is not a concern.

3. Analysis Sets

For purposes of analysis, the following populations are defined:

Table 1: Analysis sets

Population	Description
Full Analysis Set (FAS)	All participants that fulfill the criteria for screening part 1 and part 2, and received one or more full doses of RLYB212.
Neonate Full Analysis Set (NFAS)	Neonates born to participants that fulfill the criteria for screening part 1 and part 2 and received one or more doses of RLYB212.
Safety Analysis Set (SAS)	All participants in the study who received any dose of RLYB212.
RLYB212 PK Analysis Set	All participants received at least one dose of RLYB212 and at least one RLYB212-PK sample has been analyzed will be included.
Immunogenicity Analysis Set (IMAS)	All participants that fulfill the criteria for screening part 1 and part 2, received one or more doses of RLYB212 and had detection and categorization of ADA.

Population	Description
Alloimmunization Analysis Set (AAS)	All participants who had at least one screening (Screening Part 1 or 2) or baseline (Visit 2) determination of anti-HPA-1a activity and a subsequent determination of anti-HPA-1a activity postpartum.

4. Statistical Analyses

4.1. General Considerations

Continuous data will be summarized using descriptive statistics (the number of participants[n], mean, SD, median, 25th and 75th percentiles [where appropriate], minimum and maximum unless otherwise stated). For log transformed data, gmean, geometric CVmedian, minimum and maximum will be presented.

For continuous data including derived data, the minimum and maximum will be reported to the same number of decimal places as the raw data recorded in the database. The mean, median, lower quartile and upper quartile will be reported to 1 more decimal place than the raw data recorded in the database. The SD and geometric CV will be rounded to 2 additional decimal places compared to the original data. In general, the maximum number of decimal places reported will not exceed four decimal places for any summary statistic. If for any summary table, n is less than three, then only n, minimum, and maximum should be presented, and other summary statistics will be left blank.

Categorical data will be summarized in terms of the number of participants providing data at the relevant time point (n), frequency counts and percentages. Percentages will not be presented for 0 (zero) counts. Unless otherwise stated, percentages will be calculated using the number of participants included in the analysis set for that treatment group as denominator and presented to 1 decimal place.

Date variables are formatted as YYYY-MM-DD for presentation. Time is formatted in a 24 hour clock time as HH:MM for presentation.

For assessments on the day of first dose where time is not captured, a nominal pre-dose indicator, if available, will serve as evidence that the assessment occurred prior to first dose. Assessments

on the day of first dose where neither time nor a nominal pre-dose indicator are captured will be considered prior to first dose if such procedures are required by the protocol to be conducted before first dose.

Wherever possible, data will be decimal aligned.

4.1.1. Data Quality Assurance

All tables, figures, and data listings will be independently checked for consistency, integrity, and in accordance with standard Parexel procedures.

4.1.2. Software

All outputs will be produced using SAS® Version 9.4 or later in a secure and validated environment.

4.1.3. General Variables

4.1.3.1. Baseline

For all laboratory variables, vital signs, and -pharmacodynamic variables, the baseline will be the latest recorded measurement prior to the first dose of the study drug. Unless otherwise specified, any information taken after first dose/administration of study medication will be regarded as post baseline information. When time is not available, any observation on the same day as first dose will be assumed to be before first dose and may qualify as the baseline value. If more than 1 measurement is taken on the same day for a particular laboratory or vital signs parameter, the value with the later time (if available) will be considered as baseline. Otherwise, the average of the measurements taken on the same day will be used as the baseline.

In all summaries:

Change from baseline = post-baseline value - baseline value.

$$\text{Percent change from baseline} = \frac{\text{post-baseline value} - \text{baseline value}}{\text{baseline value}} \times 100.$$

4.1.3.2. Relative Day

Wherever data are summarized over time, study day will be calculated in relation to date of first treatment. If no value exists before the first dose/administration, then the baseline value will be treated as missing. Unless time variables indicate otherwise, AEs occurring on the day of first dose will be assumed to have occurred after first dose and will be assumed to be TE. The relative day for an assessment will be calculated from the first dosing date of the study drug and derived as follows:

- For days prior to the first dose = Assessment Date – first dosing date.
- For post-dose relative days = Assessment Date – first dosing date +1.

The relative day will be included in relevant listings.

4.1.3.3. Analysis Visit Window

The protocol specified visit windowing will be followed for all assessments (see [Table 3](#) and [Table 4](#)). If multiple visits occur in a time window, the one closest to the target visit will be used for analyses. If the two visits have the same distance from a target window, the later one will be used. If two or more visits have the same date and time (or a date but no time) then the average of these visits will be used. Both unscheduled and scheduled visit values will be considered (with no preference) for use in the analyses using the rules above.

4.1.3.4. Handling of Missing Data

Missing or below lower limit of quantitation (BLQ) PK results prior to the first dose of RLYB212 will be imputed as zero for graphing and descriptive statistics of concentrations. RLYB212 concentrations with missing time or date information will be considered non-evaluable, will be flagged in the data set. No formal analysis of “outliers” is planned.

No imputation of missing data will be performed except the partial date imputations specified as below:

Missing or Partial Dates

All listings will report dates as collected on the eCRF and will not include imputed dates.

Imputation Rules for Prior or Concomitant Medication Dates

Project Document Version No.:2.0; Document Effective Date: Date of last signature

TP-GDO-WW-016-09

Effective Date: 22 Dec 21

Related to: SOP-GDO-WW-019

Page 16 of 70

Missing Medication Start Date

- If the medication start date is missing, and the medication stop date is on or after the first dose of study medication, then the medication start date will be imputed as the date of the first dose of study medication.

If the medication start date is missing, and the medication stop date is not missing and before the first dose of study medication, then the medication start date will be imputed as the medication stop date.

Partial Medication Start Date

Missing Day and Month

- If the year of the incomplete start date is the same as the year of the date of the first dose of study medication, then the day and month of the date of the first dose of study medication will be assigned to the missing fields.
- If the year of the incomplete start date is before the year of the date of the first dose of study medication, then December 31 will be assigned to the missing fields.
- If the year of the incomplete start date is after the year of the date of the first dose

Missing Month Only

- The day will be treated as missing and both month and day will be replaced according to the above procedure.

Missing Day Only

- If the month and year of the incomplete start date are the same as the month and year of the date of the first dose of study medication, then the day of the first dose of study medication will be assigned to the missing day.
- If either the year is before the year of the date of the first dose of study medication or if both years are the same, but the month is before the month of the date of the first dose of study medication, then the last day of the month will be assigned to the missing day.
- If either the year is after the year of the date of the first dose of study medication or if both years are the same, but the month is after the month of the date of the

first dose of study medication, then the first day of the month will be assigned to the missing day.

Missing Medication Stop Date

- If a medication stop date is missing and the ongoing status is also missing, then the medication is assumed to be ongoing.
- If the imputed medication stop date is before the study medication start date (whether imputed or non-imputed), then the imputed medication stop date will be equal to the study medication start date.

Partial Medication Stop Date

Missing Day and Month

- If the year of the incomplete stop date is the same as the year of the date of the last dose of study medication, then the day and month of the date of the last dose of study medication will be assigned to the missing fields.
- If the year of the incomplete stop date is before the year of the date of the last dose of study medication, then December 31 will be assigned to the missing fields.
- If the year of the incomplete stop date is after the year of the date of the last dose of study medication, then January 1 will be assigned to the missing fields.

Missing Month Only

- The day will be treated as missing and both month and day will be replaced according to the above procedure.

Missing Day Only

- If the month and year of the incomplete medication stop date are the same as the month and year of the date of the last dose of study medication, then the day of the last dose of study medication will be assigned to the missing day.
- If either the year is before the year of the date of the last dose of study medication or if both years are the same, but the month is before the month of the date of the

last dose of study medication, then the last day of the month will be assigned to the missing day.

If either the year is after the year of the date of the last dose of study medication or if both years are the same, but the month is after the month of the date of the last dose of study medication, then the first day of the month will be assigned to the missing day.

Imputation Rules for Adverse Event (AE) Dates

Missing AE Start Date

- If the AE start date is missing, and the AE stop date is on or after the first dose of study medication, then the AE start date will be imputed as the date of the first dose of study medication.
- If the AE start date is missing, and the AE stop date is not missing and before the first dose of study medication, then the AE start date will be imputed as the stop date.

Partial AE Start Date

Missing Day and Month

- If the year is the same as the year of the date of the first dose of study medication, then the day and month of the date of the first dose of study medication will be assigned to the missing fields.
- If the year is before the year of the date of the first dose of study medication, then December 31 will be assigned to the missing fields.
- If the year is after the year of the date of the first dose of study medication, then January 1 will be assigned to the missing fields.

Missing Month Only

- The day will be treated as missing and both month and day will be replaced according to the above procedure.

Missing Day Only

- If the month and year are the same as the month and year of the date of the first dose of study medication, then the day of the first dose of study medication will be assigned to the missing day.
- If either the year is before the year of the date of the first dose of study medication or if both years are the same, but the month is before the month of the date of the first dose of study medication, then the last day of the month will be assigned to the missing day.
- If either the year is after the year of the date of the first dose of study medication or if both years are the same, but the month is after the month of the date of the first dose of study medication, then the first day of the month will be assigned to the missing day.
- If the imputed AE start date is after the AE stop date, then the imputed AE start date will be populated to the AE stop date.

All listings will report dates as reported on the eCRF and will not include imputed dates.

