6.6 Concomitant Therapy

Standard treatments given during obstetric care are allowed. Routine vaccines, given at recommended times during or immediately after pregnancy, will be allowed in the study.

Any medication (including over-the-counter or prescription medicines, vitamins, and/or herbal supplements) or other specific categories of interest that the participant is receiving at the time of enrollment or receives during the study must be recorded along with:

- Reason for use
- Dates of administration including start and end dates
- Dosage information including dose and frequency

The medical monitor should be contacted if there are any questions regarding concomitant or prior therapy.

Concomitant medications may be considered on a case-by-case basis by the investigator in consultation with the medical monitor.

6.6.1 *Rescue Medicine*

There are no rescue medications defined in the protocol.

6.6.2 *Excluded Treatments, Medical Devices, and/or Procedures During Study Period*

Broad spectrum immunosuppressant agents and IVIG are not allowed as concomitant medications with RLYB212 administration. If such treatments are required, RLYB212 will be discontinued but the participant will continue to be followed as described in [Section 7.1](#).

6.7 *Intervention of Overdose or Dosing Errors*

In the event of an error in dosing, including overdose, the investigator should contact the medical monitor/Sponsor immediately and closely monitor the participant for any AE/SAE and laboratory abnormalities. Where available, the quantity of the excess dose as well as the duration of the overdose should be documented. The Sponsor will determine when and if further dosing will be given, and what dose.

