4.1.4.7. Prior and Concomitant therapy

Standard treatments given during obstetric care are allowed during the study. Any medication (including over-the-counter or prescription medicines, recreational drugs, vitamins, and/or herbal

supplements) or other specific categories of interest that the participant is receiving at the time of enrollment or receives during the study will be recorded along with:

- Reason for use
- Dates of administration including start and end dates
- Dosage information including dose and frequency

Concomitant medications will be considered on a case-by-case basis by the investigator in consultation with the medical monitor.

For the purpose of inclusion in prior and/or concomitant medication summaries, incomplete medication start and stop dates will be imputed as detailed in [section 4.1.3.4.](#)

- Prior medications: Medications taken prior to study treatment with a stop date prior to first dose of study treatment.
- Concomitant medications: Medications with a stop date on or after the first dose date of study treatment (and could have started prior to or during treatment).

Prior and concomitant therapies will be summarized and listed separately for FAS. Both prior and concomitant therapy will be summarized by ATC drug class level 4 and by ATC drug class level 1 for preferred name using the number and percentage of participants. A participant reporting the same medication more than once will be counted once within each preferred name. The summary will be ordered alphabetically by ATC 4 drug class, and by preferred drug name in order of descending frequency within each ATC 1 drug class. For drugs with the same frequency, sorting will be done alphabetically.

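### SAP 4.1.3.4 resets imputed medication stop dates to the RLYB212 start date, so no medication with an imputed partial stop date can be classed as prior

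*SAP*

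**What the plan says.** SAP 4.1.3.4 has two layers of rules for medication stop dates.

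- **Completing a partial date.** The rules compare the known part with the last dose of RLYB212. With day and month missing: "If the year of the incomplete stop date is before the year of the date of the last dose of study medication, then December 31" is assigned. If the year matches the last-dose year, the last-dose date is used ("If the year of the incomplete stop date is the same as the year of the date of the last dose of study medication"). With only the day missing, a month earlier than the last-dose month is completed to its final day.
- **The reset.** The trigger reads "If the imputed medication stop date is before the study medication start date (whether imputed or non-imputed"). It is printed under the heading for missing stop dates, ahead of the partial-date rules. Once it is met, the instruction is: "then the imputed medication stop date will be equal to the study medication start date".

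SAP 4.1.4.7 then divides medications by stop date. Prior means stopped before first dose. The other class is defined as "Concomitant medications: Medications with a stop date on or after the first dose date of study treatment". The same section says that incomplete dates are imputed under 4.1.3.4 for this purpose.

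SAP 4.9 restricts the final output to participant-level listings, which include prior and concomitant medication. SAP 4.1.3.4 says that listings show dates as collected, without imputed dates.

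**The concern.** The two layers work against each other. Completing an old stop date to 31 December or to a month end has no effect on classification if any result before first dose is then moved to first dose. A date equal to first dose meets the concomitant definition and cannot meet the prior one.

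The wording points to a slip. The reset refers to a start date "before the study medication start date (whether imputed or non-imputed"), but the SAP has no rule for imputing the RLYB212 start date. It does have rules for imputing a medication's own start date. The other rules in the section speak of the first or last dose of study medication; a study medication start date appears only in this bullet. The adverse event rule in the same section compares an event's own two dates: an imputed start later than the stop is set to the stop.

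At stake is the prior/concomitant label. It carries meaning in this trial because Protocol 6.6.2 states "Broad spectrum immunosuppressant agents and IVIG are not allowed as concomitant medications with RLYB212 administration".

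**Working it through.** The plan gives no figure to reproduce. The check applies the rules literally.

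**Which dates the reset can touch.** "If a medication stop date is missing and the ongoing status is also missing, then the medication is assumed to be ongoing", and no other rule gives a wholly missing stop date a calendar date. Only partial stop dates are ever imputed, so the reset can act only on those, despite the heading above it. A date with the year missing has no rule and is left out.

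**Logic.** Let F be first dose, L last dose and I the completed stop date.

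1. If I < F, the reset sets I = F. Then I ≥ F, so the medication is concomitant.
2. If I ≥ F, the reset does not act and the medication is concomitant anyway.

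Either way it is never prior. Example: a stop date of March 2019 becomes 31 March 2019, is reset to F, and the medication is concomitant.

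**Enumeration.** The documents give no dosing dates, so four values of F were assumed, with L 24 weeks later (GW 16 to GW 40). Every true stop date from 1 to 90, 365 and 1825 days before F was run, once with day missing and once with day and month missing: 4 × 3 × 2 = 24 scenarios. All of these medications are truly prior. The literal rule made 100% of them concomitant in all 24.

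The same run without the reset shows how many become concomitant through the partial-date rules alone. Over the five-year look-back (1825 dates):

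| Assumed F | L | Day missing | Day and month missing |
|---|---|---|---|
| 15 Nov 2024 | 2 May 2025 | 14 (0.8%) | 319 (17.5%) |
| 20 Jan 2025 | 7 Jul 2025 | 19 (1.0%) | 19 (1.0%) |
| 10 Jun 2025 | 25 Nov 2025 | 9 (0.5%) | 160 (8.8%) |
| 1 Sep 2025 | 16 Feb 2026 | 0 (0.0%) | 243 (13.3%) |

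These counts have a simple source.

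- **Day missing:** a stop in the month of first dose is completed to that month's end, on or after F. The count is the day of the month of F minus 1 (for 20 January, 20 − 1 = 19).
- **Day and month missing:** a stop in the year of first dose is completed to L if L is in that year, or to 31 December if L is in a later year. Both are on or after F. The count is the day of the year of F minus 1 (15 November 2024 is day 320, so 319).

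The reset therefore accounts for the rest: at least 1825 − 319 = 1506 of 1825 (82.5%) over five years.

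**After the correction.** With the medication's own start date as the floor, the run returns exactly the counts in the table. Over the 90-day and 365-day look-backs the remainder is 0 to 21.1% (day missing) and 5.2 to 100% (day and month missing). The run took the own start date as known, 10 days before the true stop. If that start is year-only in the year of first dose, 4.1.3.4 imputes it to F, and the corrected floor would also carry an earlier imputed stop to F.

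**The case against.** The strongest reply is that very little depends on this. SAP 4.9 cancels the tables, one participant was enrolled, and imputation was specified for inclusion in summaries that will not be produced. Listings print the collected dates, so the reset date is never displayed and a misplaced line would be visible. SAP 4.1.4.7 planned separate prior and concomitant listings, but 4.9 does not say whether they stay separate. All of this stands and limits the effect to where a line is placed.

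A reader might infer that the output would show a prohibited immunosuppressant or IVIG treatment that never happened. The documents do not support that. No such record is shown to exist, and an old partial stop date would be printed as collected. The restriction in Protocol 6.6.2 operates during care, and SAP 4.1.4.2 has deviations documented in routine monitoring and classified case by case. The Screening Part 2 exclusions (ongoing immunosuppression, past or current IVIG for an underlying disease, autoimmune history) make such a record less likely.

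A reader might also infer that the reset causes every reclassification, so that correcting it restores the split. The table shows otherwise: some partial dates become concomitant before the reset is reached.

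What the reply does not remove is that the governing text, applied as written, cannot produce the split that 4.1.4.7 defines.

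**Conclusion.** The rule is wrong as written, and the impact is minor. Literally applied, it makes every medication with an imputed partial stop date concomitant. That is a statement about the rule: the number of such records in the single participant is unknown and may be zero. No endpoint or safety rate is computed from the split.

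That the medication's own start date was intended is an inference from the wording and from the parallel adverse event rule, but a strong one. The residual percentages rest on the assumed dosing dates, a 24-week dosing span and evenly spread true stop dates. They show that correcting the reset is necessary but not sufficient; they do not estimate an error rate in this trial.

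**What to change.** Reword the reset in SAP 4.1.3.4 so that a completed stop date earlier than that medication's own start date, collected or imputed, is set to that own start date. Place it after the partial-date rules and align the program.

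For what remains, flag as indeterminate, or check against the raw date, any year-only stop date in the last-dose year, or in the first-dose year when the last dose falls in a later year. Do the same for a stop date known only to the month of first dose, and for a stop date moved by an own start date that was itself imputed to first dose.

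The cost is a few words in the SAP, about one line of code, and a look at any partial stop dates for one participant. If the SAP will not be reissued, record the intended rule with the listings and confirm how any such records were classified.
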